## **5.0 Enrollment/Randomization**

All residents and Labor and Delivery staff will be apprised of the study and appropriate patients with either planned cesarean delivery or those delivered by cesarean delivery within 36 hours will have the opportunity to participate in the trial. The research team will use a daily list of all cesarean deliveries in Epic to identify potentially eligible patients for enrollment. Prior to contacting the patient, the research team member will check with the patient's nurse or care team to discuss eligibility and appropriateness for the study. Notices will also be placed in Labor and Delivery regarding the study. Study personnel will explain the study to the patient and allow ample time for the subject to ask questions related to the study. If the subject consents, she will sign the informed consent document and will be provided with a copy of the consent form prior to randomization.

Patients will be enrolled either during their delivery admission up until 36 hours after delivery. After enrolling, randomization will be performed on the obstetric unit within the first 36 hours postpartum. Participants will be randomized in a 1:1 ratio using permuted blocks of 6. RedCap will be used for randomization, using an uploaded randomization sequence. A member of the study team will access RedCap to complete randomization. The randomization result will be noted with the patient's study number and retained in the research record.

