**Exclusion criteria:**

1. Vertical skin incision
2. Inability to place device superior to incision
3. Presence of surgical drain
4. Opioid use disorder
5. Chronic opioid use ( $\geq$  14 consecutive days during pregnancy)
6. Allergy to device adhesive
7. Active COVID-19 infection
8. Patient unable to consent

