## **6.0 Study Procedures**

Methods: Patients who meet inclusion criteria and undergo cesarean delivery at Vanderbilt University Hospital center will be asked to participate. Informed consent will be obtained during the delivery admission. Enrolled patients will be randomized within the first 36 hours following cesarean delivery. The 36-hour window for randomization will begin at the completion of surgical case, as marked in the Anesthetic Care Record in the EMR.

Patients randomized to the treatment group will have the ABBY device applied by study personnel at the time of randomization, followed by continuation of usual postoperative care. The control group will have postoperative care per usual care.

Cesarean delivery will be performed by patients' surgical team, with surgical technique per surgeon preference. Women in the treatment group will have the ABBY device placed above the incision within 36 hours of cesarean delivery completion. All team members placing the ABBY device will undergo training and demonstrate competence.

Postoperative analgesia will be administered to all participants as per routine guidelines on postpartum. All study patients will receive an electronic survey at 10 days postoperatively and again at 14 days for those continuing to use the ABBY device or opioid medication at the 10-day survey.

Specific medical information regarding pregnancy and delivery will be collected and analyzed from the patients' electronic medical records.

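### A single fixed block size of 6 lets anyone who knows it and tracks every allocation deduce on average 25% of assignments (54 of 216); mixing sizes cuts this to about 2% but leaves best-guess accuracy at 68%

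*Combined protocol and SAP*

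**What the plan says.** Section 5.0 (Enrollment/Randomization) specifies "Participants will be randomized in a 1:1 ratio using permuted blocks of 6". Delivery is by a pre-made list: "RedCap will be used for randomization, using an uploaded randomization sequence". No strata and no variation in block size are mentioned anywhere in the protocol.

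Section 6.0 (Study Procedures) describes one hospital. On the device arm, "Patients randomized to the treatment group will have the ABBY device applied by study personnel at the time of randomization". On the other arm, "The control group will have postoperative care per usual care". No sham device is described.

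Three provisions bear on who enters and when:

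- Before contact, the research team member consults the nurse or care team "to discuss eligibility and appropriateness for the study" (section 5.0). Appropriateness is not defined.
- Consent comes first, and then "After enrolling, randomization will be performed on the obstetric unit within the first 36 hours postpartum" (section 5.0).
- Section 6.0 states the intended rule for approach: "Patients who meet inclusion criteria and undergo cesarean delivery at Vanderbilt University Hospital center will be asked to participate".

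Section 4.0 excludes "Opioid use disorder" and chronic opioid use. Section 10.0 sets the sample at 108 per group, 216 in total. Section 2.0 names postoperative opioid use as the primary outcome.

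**The concern.** With a single known block size, a complete record of past allocations fixes some future ones. The last slot of every block is always determined, and earlier slots are determined whenever one arm has used its three places. REDCap hides the rest of the list but cannot hide what follows by subtraction. Because the device is visible and study staff apply it, the enrolling team could hold both pieces of information: the block size from the protocol and the allocations from daily work.

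A person who knows the next arm could, deliberately or not, let it influence whether a woman is judged appropriate to approach, or when within the 36-hour window a consented woman is randomised. Women may be approached up to 36 hours after delivery, when their early postoperative course may already be known to the care team. That course plausibly relates to later opioid use, the primary outcome. Selection of this kind would unbalance the arms in a way that randomisation is meant to prevent.

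**Working it through.** **Inputs.** Block size 6 at 1:1, so three per arm per block (section 5.0). Total 216 (section 10.0), so 216 / 6 = 36 complete blocks. One unstratified list is assumed, since section 5.0 names no strata. The plan gives no predictability figure to reproduce.

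**Certain allocations in one block.** There are C(6,3) = 20 equally likely blocks. Counting the allocations that are forced because one arm is used up:

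| Forced allocations | Blocks |
|---|---|
| 1 | 12 |
| 2 | 6 |
| 3 | 2 |

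Mean = (12×1 + 6×2 + 2×3) / 20 = 30/20 = 1.5 of 6 = 25%. The closed form 2m/(m+1) with m = 3 per arm also gives 1.5. By position, slot 6 is always forced, slot 5 in (6+2)/20 = 40% of blocks, and slot 4 in 2/20 = 10%.

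**Whole trial.** Mean 36 × 1.5 = 54 of 216. Per-block variance = (12×1 + 6×4 + 2×9)/20 − 1.5² = 2.7 − 2.25 = 0.45, so the SD is √(36 × 0.45) = 4.0. The exact distribution over 36 blocks puts the central 95% at 46 to 62. The possible range is 36 (one per block) to 108 (three per block).

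**Best guess, fixed blocks of 6.** Expected correct guesses per block = m + (2^(2m)/C(2m,m) − 1)/2 = 3 + (64/20 − 1)/2 = 4.1, and 4.1/6 = 68.3%.

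**Randomly varying sizes.** Trials of 216 were simulated with sizes drawn with equal probability. The observer knows the set of sizes but not their order, sees every allocation, and updates by Bayes' rule. An allocation counts as certain only if every block state consistent with the record forces it.

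| Sizes | Certain, of 216 | Share | Best guess |
|---|---|---|---|
| 6 only (exact) | 54 | 25% | 68.3% |
| 4, 6, 8 (3,000 trials) | 5.1 | 2.3% | 68.0% |
| 4, 6 (2,000 trials) | 12.0 | 5.5% | 69.3% |
| 6, 8 | 8.2 | 3.8% | 67.2% |
| 4, 8 | 16.3 | 7.5% | 68.0% |

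For 4, 6 and 8, 95% of simulated trials had 0 to 14 certain allocations. Separate runs gave 2.2% to 2.4%. If the set of sizes is also unknown, nothing can be deduced with certainty. If the size in use were known at the start of each block, certainty would return to (4/3 + 3/2 + 8/5)/18 = 24.6%, so hiding the order is essential.

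**Why the best guess does not improve.** Guessing the arm that is currently behind needs only a running tally. That rule scores 68.3% under fixed 6 and 68.0% under 4, 6 and 8.

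**Incomplete tracking.** With a fixed 6, certainty requires having seen all three allocations to the exhausted arm. If each past allocation is seen independently with probability q, and the observer still knows where blocks begin, the certain share is 0.25 × q³: 18.2% at q = 0.9, 10.5% at q = 0.75 and 3.1% at q = 0.5. These values of q are assumptions.

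**Imbalance.** With 4, 6 and 8 stopped at 216, the final difference between arms averaged 0.56 patients. It cannot exceed 4, half the largest block.

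**The case against.** The strongest objection is that the change hardly affects guessing. At 68.3% against 68.0%, the expected correct guesses are 147.6 and 146.9 of 216, a difference of less than one. Someone inclined to steer enrolment may act on a good guess and does not need certainty. This stands, and it limits the benefit to allocations known outright.

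Second, 54 is the average for an observer with full information. One person would have to know the size, hold every allocation in order, and influence who is approached or when. Section 5.0 spreads these tasks over a research team member, the care team and whoever operates REDCap, and no tally is documented. This also stands. With partial tracking the share falls quickly, as the 0.25 × q³ figures show.

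Third, the room to act is narrow. Women who meet the criteria are to be asked, consent precedes randomisation, others may be randomised in between, and opioid use disorder and chronic opioid use are excluded. Some room remains. The appropriateness check is undefined and the 36-hour window is flexible. Section 10.0 implies 1400 × 0.8 × 0.5 = 560 participants a year, about 1.5 a day, while 216 over 12 months is about 0.6 a day. Over 36 hours (1.5 days) that is roughly 0.9 to 2.3 enrolments, slow enough to follow and enough for waiting to change a woman's slot.

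Fourth, withholding a fixed size of 6 might achieve part of the gain without a new list. That is fair, and its share of the gain was not computed. However, the size is already printed in the protocol, and under a fixed 6 the tally balances after every sixth allocation, so a careful observer might recover it.

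**Conclusion.** The point holds as an inexpensive improvement worth considering, not as an error in the plan. Under fixed blocks of 6, an average of 25% of allocations (54 of 216) could be known in advance. Sizes of 4, 6 and 8 in random order would reduce this to about 2% (about 5 of 216). Best-guess accuracy stays at about 68%.

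The 25% assumes one unstratified list, a known block size and complete tracking. The 2% assumes equally likely sizes and an observer who knows the set but not the order. No size of bias is given: the documents state no outcome scale or SD, and any selection effect would be invented. Nothing in the documents shows that selection occurred.

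**What to change.** Upload to REDCap a sequence whose block sizes vary at random, for example 4, 6 and 8 in random order. Replace the sentence in section 5.0 with one saying that randomly varying permuted blocks are used, and keep the sizes in a document that enrolling staff do not use. Three sizes do better than any of the two-size sets examined. It would be convenient to state in the same edit who prepares and holds the sequence, which the supplied text does not say.

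Before enrolment this costs one new upload file and one edited sentence. If enrolment has begun, replacing the unused part of the active sequence should be a documented change to the randomisation procedure. The statistical price is losing the exact 108/108 split that 36 blocks of 6 would give, which is negligible at this sample size.

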## **6.0 Study Procedures**

Methods: Patients who meet inclusion criteria and undergo cesarean delivery at Vanderbilt University Hospital center will be asked to participate. Informed consent will be obtained during the delivery admission. Enrolled patients will be randomized within the first 36 hours following cesarean delivery. The 36-hour window for randomization will begin at the completion of surgical case, as marked in the Anesthetic Care Record in the EMR.

Patients randomized to the treatment group will have the ABBY device applied by study personnel at the time of randomization, followed by continuation of usual postoperative care. The control group will have postoperative care per usual care.

Cesarean delivery will be performed by patients' surgical team, with surgical technique per surgeon preference. Women in the treatment group will have the ABBY device placed above the incision within 36 hours of cesarean delivery completion. All team members placing the ABBY device will undergo training and demonstrate competence.

Postoperative analgesia will be administered to all participants as per routine guidelines on postpartum. All study patients will receive an electronic survey at 10 days postoperatively and again at 14 days for those continuing to use the ABBY device or opioid medication at the 10-day survey.

Specific medical information regarding pregnancy and delivery will be collected and analyzed from the patients' electronic medical records.

## **7.0 Risks**

A rare risk exists if the patient has an unknown allergy to the adhesive material in the device, though this is estimated at less than one per one million for the silicone-based adhesive used, and per the manufacturer's report, the raw materials used in the silicone roll stock construction (PS-1860) have been analyzed for biocompatibility and found to not cause any adverse effect when used properly (Polymer Science, Monticello, IN).

There is a risk of confidentiality breech in the collection of medical information. All efforts will be made to protect the personal information of the patient by the use of study number assignment and a password-protected database. Any breech in confidentiality will be promptly reported to the Vanderbilt IRB.

## **8.0 Reporting of Adverse Events or Unanticipated Problems involving Risk to Participants or Others**

Any adverse events will be reported to the Institutional Review Board in a timely manner as appropriate.

## **9.0 Study Withdrawal/Discontinuation**

Any patient who wishes to withdraw from the study will be allowed to withdraw. Should the patient decide to withdraw from the study, she will notify the principal investigator and her information will be deleted from the study records.

## **10.0 Statistical Considerations**

Sample size: To detect a reduction in pain medication use of 40% using an alpha of 0.05 and a beta of 0.20, 108 patients per group with a total sample of 216 patients will be required. The labor and delivery unit performs about 1400 cesarean deliveries annually; therefore, assuming an 80% eligibility rate and subsequent 50% participation rate, the study would be conducted over a 12-month period.

## **11.0 Privacy/Confidentiality Issues**

Risks to participants are minimized by limiting this prospective study to subjects meeting the inclusion/exclusion criteria. Access to PHI will be limited to the PI and co-investigators. All patients will be de-identified by assignment of a study number. All data collected in this study will be kept electronically in a secure REDCap database. The primary risk in this study involves the disclosure of protected health information. This risk is reasonable, given the above precautions, in relation to the potential benefit to both future patients and society in general by the possibility of reducing the use of pain medication in cesarean patients.

